1.0 BACKGROUND AND RATIONALE

1.1 Study Synopsis

The purpose of the study is to assess the utility of combined, simultaneous positron emission tomography (PET) and magnetic resonance imaging (MRI), collectively called PET-MR, in assessing response to neoadjuvant chemotherapy and surgical treatment decisions for operable breast cancers. Adult patients with operable breast cancer that are being treated at UNC with neoadjuvant chemotherapy followed by potentially curative surgical resection will be identified through the Multidisciplinary Breast Tumor Board. Patients who are being treated with neoadjuvant chemotherapy followed by surgical resection and for whom pre- and post-treatment MR imaging is part of planned treatment will undergo additional pre-treatment and post-treatment PET/MR. The response to treatment will be assessed at post-treatment by evaluating change in tumor size from MRI, change in response to dynamic contrast enhanced (DCE) MRI, and 18F-fluorodeoxyglucose (18F-FDG) avidity from PET. Patients will then undergo surgery. Their pathology will be reviewed for treatment effect as assessed by residual cancer burden (RCB) score. Patients will be followed and assessed for recurrence.

This study is designed to provide preliminary information on the progression of tumor size, DCE-MRI response, and FDG avidity during and after treatment in 25 patients diagnosed with operable breast cancer. The primary objective is to evaluate the capabilities of MRI/PET in prediction of RCB score as compared to standard-of-care MRI alone. A secondary objective will be to quantify the progression of PET- and MRI-based quantitative metrics at pre-, and post-treatment time points, and correlate these quantitative measures with RCB score.

Information from this study may be used to estimate effect size for power calculation and sample size considerations for possible future studies in the use of combined PET-MR to be used in determination of which patients are candidates for breast-conserving surgery versus mastectomy. Existing studies point to the possibility of this combined imaging information enabling more patients to be candidates for breast-conserving surgery with no impact to recurrence rate.

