2.2 Secondary objectives

- 2.2.1** To estimate the correlation between changes from pre-treatment to post-treatment in the Metabolic Tumor Volume metric from PET acquired on the PET-MRI scanner and the Residual Cancer Burden score from the pathology report;

- 2.2.2** To evaluate metrics combining multiple features from simultaneous positron emission tomography (PET maximum SUV, metabolic tumor volume, total lesion glycolysis) and magnetic resonance imaging (MRI tumor size, DCE quantitative measures) in early prediction of response to neoadjuvant chemotherapy at pre-treatment and post-treatment time points.

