For all PET scans, patients will be instructed to fast, and blood glucose levels will be measured prior to imaging. Patients will be injected with 10 mCi 18F-FDG, and then imaged starting 60 minutes post-injection for ten minutes each at one or two bed positions focused on the primary tumor site. MRI sequences to be run will include conventional anatomic T1- and T2-weighted sequences, high-resolution T1 pre- and post-contrast DCE sequences, and the Dixon PET-MR attenuation-correction sequence.

The PET-MRs at each time point will be evaluated retrospectively by UNC radiologists as to the size of the lesion, the FDG activity as measured by tumor-maximum and tumor-mean standard uptake values (SUVs), additional PET metrics (metabolic tumor volume (MTV) and total lesion glycolysis (TLG)), the presence or absence of invasion to adjacent organs, and the presence or absence of metastatic or multifocal disease. PET images will be evaluated with aligned anatomical MRI for guidance as well as determination of the tumor margins for computation of tumor-mean SUV.

The PET/MRs will be evaluated by UNC breast radiologists and nuclear medicine specialists as to the size of the lesion, the FDG activity as measured by SUV_{max} and SUV_{mean}, the presence or absence of invasion to adjacent organs, and the presence or absence of metastatic or multifocal disease. The pathological specimens will be evaluated by a UNC pathologist specialized in breast cancer as to (1) the size of the primary tumor, (2) the proportion of invasive carcinoma within the primary tumor

bed, (3) the number of axillary lymph nodes involved, and (4) the size of the largest metastasis in an axillary lymph node. These four quantities will be used to compute the RCB score¹. Again, all data will be stored on a secured, password protected server.

¹<http://www3.mdanderson.org/app/medcalc/index.cfm?pagename=jsconvert3>

To address the primary endpoint, image metrics from the MRI component of PET-MRI and clinical MRI will be evaluated. The principal metric to be examined is the change in tumor size from pre- to post-treatment. The change in tumor size will be correlated with RCB scores reported by the pathologist.

For the secondary endpoints, quantitative imaging measures (mean SUV, maximum SUV, MTV, TLG, MRI-based tumor volume, MRI DCE imaging parameters) will be compounded for all patients. The fractional change from pre-treatment to post-treatment will be computed for all quantities.

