7.3 Data Analysis Plans

For the primary endpoint, each subject's change in tumor size will be correlated with the primary outcome (RCB score) and correlation estimated using the Pearson product-moment correlation coefficient. Confidence intervals on the correlation coefficient will be estimated using the Fisher transformation.

For secondary endpoint 2.2.1, the change from pre- to post-treatment in metabolic tumor volume (MTV) from PET imaging will be correlated with RCB score using the Pearson product-moment correlation coefficient. Confidence intervals on the correlation coefficient will be estimated using the Fisher transformation.

For secondary endpoint 2.2.2, each subject's set of quantitative measures will be compiled and an optimal linear regression between the image metrics and the outcome measure (RCB score) will be derived. Prediction performance will be evaluated using a leave-one-out cross-validation strategy.

For correlating individual metrics with RCB scores, with $n = 25$ subjects, we will have approximately 73% power to detect a Pearson correlation of at least 0.5, assuming a two-sided Type I error rate of 0.05 and utilizing the correlation test.

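### Is the Fisher interval for the correlation of MTV change with RCB too narrow if complete responders pile up at the lower bounds?

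*Combined protocol and SAP*

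**What the plan says.** Section 2.2 frames objective 2.2.1 as estimation: "To estimate the correlation between changes from pre-treatment to post-treatment in the Metabolic Tumor Volume metric" and RCB. Section 7.3 gives the method: "metabolic tumor volume (MTV) from PET imaging will be correlated with RCB score using the Pearson product-moment correlation coefficient". It then says of the interval: "Confidence intervals on the correlation coefficient will be estimated using the Fisher transformation". The same section states that with 25 subjects "we will have approximately 73% power to detect a Pearson correlation of at least 0.5", two-sided at 0.05.

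Section 7.1 sets the scale for the secondary measures: "The fractional change from pre-treatment to post-treatment will be computed for all quantities". Of the four pathology measurements (tumor size, proportion invasive, nodes involved, largest nodal metastasis) it says: "These four quantities will be used to compute the RCB score". The formula itself is reached through a web link and is not in the text.

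The plan has no rule for a lesion that is no longer FDG-avid after treatment, no MTV segmentation threshold, and no rank-based or resampling analysis alongside Pearson's r.

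**The concern.** The Fisher interval uses a standard error of 1/sqrt(n-3) for z = atanh(r), which is right for bivariate normal data. Here both variables have a floor. If a lesion disappears on PET and MTV is recorded as zero, the fractional change is exactly -100%. If no residual disease is found, RCB presumably takes its minimum. Complete response is clearly foreseen: section 3.2 excludes neoadjuvant endocrine therapy because complete response is unlikely with it, and section 1.2 discusses complete imaging response. A cluster of patients at the same corner of the scatterplot could make z more variable than the formula allows.

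What is at stake is the lower limit. Section 1.1 says: "Information from this study may be used to estimate effect size for power calculation and sample size considerations for possible future studies". A lower limit that lies above the true correlation too often could lead a later trial to plan on too strong an association.

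A related worry is coding. If a vanished lesion were treated as missing and not as zero, complete responders would leave the analysis altogether.

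**Working it through.** **Inputs from the documents.** n = 25 completers (section 7.2); two-sided 0.05 and r = 0.5 (section 7.3); fractional change for secondary measures (section 7.1).

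**Assumptions, not in the documents.** The share of patients at the bound; RCB at its minimum when there is no residual disease; MTV equal to zero when no avid lesion remains.

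**Planned power.** Phi(atanh(0.5) × sqrt(22) - 1.96) = Phi(0.5493 × 4.690 - 1.96) = Phi(0.616) = 0.731. The stated 73% reproduces.

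**Planned interval at an observed r of 0.5.** The standard error is 1/sqrt(22) = 0.213. The limits on the z scale are 0.549 ± 1.96 × 0.213, that is 0.131 and 0.967, so r runs from 0.13 to 0.75.

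**Coverage of the nominal 95% Fisher interval, simulated at n = 25.** Latent r is the correlation before values are cut off at the floor.

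| Assumed shape | Share at bound | Coverage |
|---|---|---|
| Bivariate normal, r 0 / 0.5 / 0.7 | none | 94.7 / 94.8 / 95.0% |
| Each variable cut off at its floor, latent r 0.5 / 0.7 | 20% | 93.7 / 93.1% |
| Same | 30% | 92.1 / 91.2% |
| Same | 50% | 87.3 / 85.2% |
| Same, latent r 0 | 20-50% | 94.9-95.4% |
| Patients at both floors together, r 0 / 0.5 in the rest | 20% | 93.9 / 92.6% |
| Same | 30% | 93.7 / 91.4% |
| Same | 50% | 90.6 / 86.5% |
| Cluster at both floors set apart by a gap | 20-30% | 90.7-94.8% |
| Cluster at both floors, bounded residual MTV fraction in the rest | 10-40% | 93.7-95.5% |
| Only RCB tied | 25-40% | 95.1-96.0% |
| Many patients with residual disease also at MTV zero | varied | 95.9-97.4% |
| Absolute instead of fractional MTV change | no common floor | 95.1-95.5% |

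If pathologic complete responders keep a small, non-zero MTV, separate runs gave 93.1 to 94.9% and 95.5 to 96.1%, depending on the spread of the remaining patients.

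**Lower limit.** In the two main tied models it exceeds the true r in 3.7 to 5.1% of trials at 20% tied and 4.6 to 6.5% at 30%, against a nominal 2.5%.

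**What that means for the interval.** With complete responders at both floors (10 to 40%) and a normal spread in the rest, the true standard deviation of z was 1.03 to 1.17 times the formula value. A factor of 1.1 at r = 0.5 gives 0.549 ± 1.1 × 0.418, that is 0.090 and 1.009, so r runs from 0.09 to 0.77 in place of 0.13 to 0.75.

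**Would a wider interval help?** Take the larger of 1/sqrt(n-3) and the jackknife standard error of z. At 20 to 30% tied, coverage becomes 94.7 to 96.0% in the main models. Under normality it is 96.1%, with median width 0.65 against 0.61 at r = 0.5. In the shapes where the Fisher interval is already conservative it reaches 96.3 to 97.9%. It includes zero while the planned test is significant in 6% of trials under normality at r = 0.5, and in 13% at 30% censored with latent r 0.5.

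**Coding of a vanished lesion, 30% tied.** Coding it missing instead of zero moves r from 0.46 to 0.38 (censoring, latent r 0.5) or from 0.47 to 0.00 (cluster at both floors, no association in the rest). It leaves about 25 × 0.7 = 17.5 patients.

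**The case for a change.** The strongest case for a change has two parts. First, independent simulations agree that the interval undercovers in several reasonable models. An added interval that contains the planned one by construction cannot cover less, and costs a few lines. That is true, but it puts two 95% intervals on one parameter, and the second can disagree with the planned test. It is needlessly wide wherever the Fisher interval is already sound. Spearman's coefficient with a bootstrap interval covers well (93.5 to 95.3%) but measures something else: with 30% at both floors and no association in the rest it is 0.65 against a Pearson r of 0.47.

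Second, the vanished-lesion rule does not depend on coverage at all and could alter the estimate appreciably. This is the better half of the objection, and the gap is real. But section 7.1 has the measures assembled for every patient and a fractional change computed for each quantity. A lesion with no remaining avid volume has an MTV of zero, and (0 - pre)/pre = -1. Discarding the best responders as missing would run against that text. The fall to 0.00 also needs a model with no association at all outside the cluster.

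Section 7.3 speaks of change where section 7.1 speaks of fractional change. For the secondary measures section 7.1 settles this. For the primary endpoint ("The principal metric to be examined is the change in tumor size from pre- to post-treatment") the scale is left open, which is a separate matter and does not show that the primary interval is affected.

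**Conclusion.** No change follows. The Fisher interval for 2.2.1 can be modestly too narrow, by about 1 to 4 points of coverage at an assumed 20 to 30% of patients at the bound. That requires ties at both floors together with certain spreads in the remaining patients. Under other plausible shapes it is nominal or conservative, and the documents do not decide between them. The larger losses at 50% tied rest on a share for which the documents give no support.

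The estimate is not inflated, the test and the 73% power stand, and an interval of roughly 0.13 to 0.75 at r = 0.5 already warns anyone planning a later trial. The jackknife-widened interval is a matter of preference, and a rank correlation would be an optional extra for a different quantity. Recording -100% for a vanished lesion and reporting how many patients sit at each bound is ordinary analytic practice, consistent with section 7.1 as written. The conclusion would deserve another look only if far more than 30% of patients proved to be tied at both bounds.

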7.4 Data Management

Image datasets will be stored on a secure server in the Biomedical Research Imaging Center with patient identifiers removed. De-identified copies of these may be stored temporarily on password-protected computers or portable hard drives for use in data analysis. Quantitative data extracted from the images and results of data analysis will be maintained on a secure server. All data will be archived on a password-protected computer in the office of the PI and backed up with a RAID system. Datasets will be maintained for at least five years from the close of the study.

8.0 STUDY MANAGEMENT

8.1 Institutional Review Board (IRB) Approval and Consent

It is expected that the IRB will have the proper representation and function in accordance with federally mandated regulations. The IRB should approve the consent form and protocol.

In obtaining and documenting informed consent, the investigator should comply with the applicable regulatory requirement(s), and should adhere to Good Clinical Practice (GCP) and to ethical principles that have their origin in the Declaration of Helsinki.

Before recruitment and enrollment onto this study, the patient will be given a full explanation of the study and will be given the opportunity to review the consent form. Each consent form must include all the relevant elements currently required by the FDA Regulations and local or state regulations. Once this essential information has been provided to the patient and the investigator is assured that the patient understands the implications of participating in the study, the patient will be asked to give consent to participate in the study by signing a IRB-approved consent form.

Prior to a patient's participation in the trial, the written informed consent form should be signed and personally dated by the patient and by the person who conducted the informed consent discussion.

8.2 Required Documentation

Before the study can be initiated at any site, the following documentation must be provided to the Clinical Protocol Office (CPO) at the University of North Carolina.

- A copy of the official IRB approval letter for the protocol and informed consent
- CVs and medical licensure for the principal investigator and any associate investigators who will be involved in the study
- A copy of the IRB-approved consent form

8.3 Registration Procedures

Once patients have consented to be a subject in this trial, they will be assigned an encoded false patient name/number, such as "BR_001". This identifier will be used

throughout the study in the data analysis. The study coordinator will have the key to relate the patient's true name to the study identifier, and will coordinate the acquisition and de-identification of relevant clinical patient data so that study personnel not directly involved in patient care will not have access to any personally identifiable information. The study coordinator will secure all information related to patient identifiers on a restricted-access, password-protected computer.

All patients must be registered with a study coordinator at the University of North Carolina Biomedical Research Imaging Center before enrollment in the study. The Study Coordinator will verify that the patient meets all criteria to participate in the study before registration.

8.4 Adherence to the Protocol

Except for an emergency situation in which proper care for the protection, safety, and well-being of the study patient requires alternative treatment, the study shall be conducted exactly as described in the approved protocol.

8.4.1 Emergency Modifications

UNC investigators may implement a deviation from, or a change of, the protocol to eliminate an immediate hazard(s) to trial subjects without prior UNC IRB approval.

For any such emergency modification implemented, a UNC IRB modification form must be completed by UNC Research Personnel within five (5) business days of making the change.

8.4.2 Single Patient/Subject Exceptions

Any request to enroll a single subject who does not meet all the eligibility criteria of this study requires the approval of the UNC Principal Investigator and the UNC IRB.

8.4.3 Other Protocol Deviations/Violations

According to UNC's IRB, a protocol deviation is any unplanned variance from an IRB approved protocol that:

- Is generally noted or recognized after it occurs
- Has no substantive effect on the risks to research participants
- Has no substantive effect on the scientific integrity of the research plan or the value of the data collected
- Did not result from willful or knowing misconduct on the part of the investigator(s).

An unplanned protocol variance is considered a violation if the variance meets any of the following criteria:

- Has harmed or increased the risk of harm to one or more research participants.
- Has damaged the scientific integrity of the data collected for the study.

- Results from willful or knowing misconduct on the part of the investigator(s).
- Demonstrates serious or continuing noncompliance with federal regulations, State laws, or University policies.

If a deviation or violation occurs please follow the guidelines below:

Protocol Deviations: UNC personnel will record the deviation in OnCore® (or other appropriate database set up for the study), and report to any sponsor or data and safety monitoring committee in accordance with their policies. Deviations should be summarized and reported to the IRB at the time of continuing review.

Protocol Violations: Violations should be reported by UNC personnel within one (1) week of the investigator becoming aware of the event using the same IRB online mechanism used to report Unanticipated Problems.

Unanticipated Problems:

Any events that meet the criteria for “Unanticipated Problems” as defined by UNC’s IRB (see section 6.3.1) must be reported by the Study Coordinator using the IRB’s web-based reporting system.

8.5 Amendments to the Protocol

Should amendments to the protocol be required, the amendments will be originated and documented by the Principal Investigator at UNC. It should also be noted that when an amendment to the protocol substantially alters the study design or the potential risk to the patient, a revised consent form might be required.

The written amendment, and if required the amended consent form, must be sent to UNC’s IRB for approval prior to implementation.

8.6 Record Retention

Study documentation includes all Case Report Forms, data correction forms or queries, source documents, Sponsor-Investigator correspondence, monitoring logs/letters, and regulatory documents (e.g., protocol and amendments, IRB correspondence and approval, signed patient consent forms).

Source documents include all recordings of observations or notations of clinical activities and all reports and records necessary for the evaluation and reconstruction of the clinical research study.

Government agency regulations and directives require that all study documentation pertaining to the conduct of a clinical trial must be retained by the study investigator. In the case of a study with a drug seeking regulatory approval and marketing, these documents shall be retained for at least two years after the last approval of marketing application in an International Conference on Harmonization (ICH) region. In all other cases, study documents should be kept

on file until five years after the completion and final study report of this investigational study.

8.7 Obligations of Investigators

The Principal Investigator is responsible for the conduct of the clinical trial at the site in accordance with Title 21 of the Code of Federal Regulations and/or the Declaration of Helsinki. The Principal Investigator is responsible for personally overseeing the treatment of all study patients. The Principal Investigator must assure that all study site personnel, including sub-investigators and other study staff members, adhere to the study protocol and all FDA/GCP/NCI regulations and guidelines regarding clinical trials both during and after study completion.

The Principal Investigator at each institution or site will be responsible for assuring that all the required data will be collected and entered onto the Case Report Forms. Periodically, monitoring visits will be conducted and the Principal Investigator will provide access to his/her original records to permit verification of proper entry of data. At the completion of the study, all case report forms will be reviewed by the Principal Investigator and will require his/her final signature to verify the accuracy of the data.

